Fluid replacement and antimicrobial therapy are the mainstays of therapy of moderate to severe cholera. Antimicrobials reduce the volume and the duration of diarrhea by half. This in turn reduces the need for rehydration fluid and shortens the duration of hospitalization. Moreover, they shorten the duration of fecal excretion of *V. cholerae* and reduce transmission of infection to others [3-5]. All of these effects make antimicrobial therapy of cholera a cost-effective intervention.

Tetracycline, chloramphenicol, doxycycline, furazolidone, trimethoprim-sulfamethoxazole and erythromycin are all effective in the treatment of cholera when given for 3-5 days [3,6-8]. Single dose tetracycline and doxycycline therapy are also effective in the treatment of cholera, although bacterial eradication is slower than with multiple dose therapy. Ciprofloxacin is also effective in the treatment of cholera in multiple doses, and we have recently demonstrated that a single dose of ciprofloxacin is more effective than single dose doxycycline therapy of cholera in adults [9]. Tetracycline and doxycycline, however, are not recommended for use in children <8 years of age, and in pregnant and lactating women; chloramphenicol is a relatively toxic drug; and newer quinolones including ciprofloxacin are not recommended for routine use in children. Although of toxicity with any of these drugs is small when used for short courses of therapy, such as with cholera, there remains a reluctance to use these drugs in children, and they often are not available in a liquid formulation that would assist in administration to children.

Treatment of cholera in children has been further complicated by the emergence of multiply-resistant strains of *V. cholerae*. Strains resistant to tetracycline (which also implies resistance to doxycycline), furazolidone (the drug that has been most commonly used to treat childhood cholera), and trimethoprim-sulfamethoxazole have been reported from Asia (including Bangladesh), Africa and Latin America [10-17]. Currently, over 90% of the *V. cholerae* O1 isolates at the treatment centres of ICDDR,B are resistant to trimethoprim-sulfamethoxazole and furazolidone, and approximately 30% are resistant to tetracycline.

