3.8 Handling of Treatment Failures

If the study treatment is judged to have failed clinically patients will be treated for 3 days with an agent other than azithromycin or erythromycin to which the isolate of *V. cholerae* will be found to be susceptible to. The treatment code will not be broken for these patients. Patients with microbiological failure will be treated with a suitable drug as determined by antimicrobial susceptibility of such isolates.

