7. DEFINITIONS

- 7.1 **Clinical success:** Cessation of watery stool within 96 hours of administration of the study drug without relapse
- 7.2 **Clinical failure:** Continuation of watery stool for > 96 hours
- 7.3 **Clinical relapse:** Cessation of watery stool within 96 hours of administration of the study drugs, its absence for 24 hours or more, and its recurrence anytime during study or between discharge and follow up 7 days from the time of discharge.
- 7.4 **Bacteriological success:** Eradication of the infecting *V. cholerae* organism from fecal specimens within 48 hours of initiation of study drugs without its subsequent isolation
- 7.5 **Bacteriological failure:** Isolation on study day 3 or thereafter from fecal samples of the study patients the same biotype and serotype of *V. cholerae* as was isolated on admission.
- 7.6 **Bacteriological relapse:** Failure to isolate the infecting *V. cholerae* from stool specimen on two consecutive study days, followed by its isolation any time after this, including at the follow-up visit.
- 7.7 **Reinfection:** Isolation of a different biotype or serotype of *V. cholerae* as was isolated on admission, or of the same biotype and serotype with a different antimicrobial susceptibility pattern.
- 7.8 **Duration of diarrhea:** The interval between administration of study drugs to the end of the last 6-hour period the patient had a watery stool.

Facilities Available

Describe the availability of physical facilities at the place where the study will be carried out. For clinical and laboratory-based studies, indicate the provision of hospital and other types of patient's care facilities and adequate laboratory support. Point out the laboratory facilities and major equipments that will be required for the study. For field studies, describe the field area including its size, population, and means of communications. (TYPE WITHIN THE PROVIDED SPACE).

Site: The Research Ward of the Dhaka Hospital of ICDDR,B will be used for hospitalization of the study children. This facility is being used for similar clinical trials for decades.

Study population: The Dhaka Hospital provides treatment to over 110,000 diarrheal patients each year, about 70% of whom are children <15 years of age. Cholera is endemic in Bangladesh, and thousands of children with cholera are treated at this hospital each year; study children will be selected from among them.

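### Clinical success is scored without regard to the further antibiotic that section 3.8 gives for a positive culture on day 3 or later, which can dilute a clinical difference and favour equivalence

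*Protocol*

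**What the plan says.** Protocol section 3.8 deals with two kinds of failure. Children judged to have failed clinically receive three days of a drug that may be neither azithromycin nor erythromycin. For the second kind it says: "Patients with microbiological failure will be treated with a suitable drug as determined by antimicrobial susceptibility of such isolates". It gives no start time for this treatment and does not repeat the bar on the study drugs.

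Section 7 supplies the definitions:

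- Clinical success (7.1): "Cessation of watery stool within 96 hours of administration of the study drug without relapse".
- Clinical failure (7.2): "Continuation of watery stool for > 96 hours".
- Clinical relapse (7.3): watery stool stops within 96 h, stays away for at least a day, and returns, counting "its recurrence anytime during study or between discharge and follow up 7 days from the time of discharge".
- Bacteriological success (7.4): clearance of the infecting "organism from fecal specimens within 48 hours of initiation of study drugs without its subsequent isolation".
- Bacteriological failure (7.5): "Isolation on study day 3 or thereafter from fecal samples of the study patients", of the same biotype and serotype as on admission.

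Clinical and bacteriologic success are both primary outcomes (section 4.1). The sample size rests on clinical success alone (section 3.6). Neither section 7 nor the Data Analysis section says how a child who received an additional antibiotic is scored, censored or excluded.

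**The concern.** Sections 3.8 and 7 interact. A positive culture from day 3 leads to more antibiotic treatment, and the clinical endpoint is then read without asking whether that treatment was given. Two kinds of children meet definition 7.1 as written although the study drug may not have earned the result:

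- a child still passing watery stool on day 3 whose stool stops by 96 h after the added drug;
- a child whose stool had already stopped and in whom the added drug prevents a relapse before follow-up.

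Added treatment follows slow clearance. If the arm that clears more slowly also does worse clinically, it receives more of this help and its clinical success rate rises towards that of the other arm. In a trial that hopes to show similar efficacy, that bias favours the hypothesis. Duration of diarrhoea, daily resolution, stool volume and relapse after day 3 are exposed in the same way.

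**Working it through.** **1. The plan's own figure.** Section 3.6 gives P = 0.95, Z_alpha = 1.645, d = 0.10 and a type II error of 20% (Z_beta = 0.8416):

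n = 2 × 0.95 × 0.05 × (1.645 + 0.8416)² / 0.10² = 58.74 per arm.

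The protocol states 58, so the figure reproduces apart from rounding. The test is one-sided at 5% with a 10-point limit.

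**2. Timing.** Section 3.5 starts the clock at the first dose and counts study days in 24 h periods, so day 3 is 48 to 72 h. Section 3.7 schedules a rectal swab every day in hospital. The documents give no culture or susceptibility turnaround. Assuming 24 to 48 h, treatment after a day-3 specimen starts between 48 + 24 = 72 h and 72 + 48 = 120 h, from 24 h before the 96 h cut-off to 24 h after it. After a day-4 specimen (72 to 96 h) it starts at 96 h at the earliest. The 96 h part of the endpoint is therefore exposed only in part. The relapse part runs to 7 days after discharge from a five-day stay, so it is mostly observed after any added treatment.

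**3. Size on the clinical outcome.** The documents give neither a bacteriologic failure rate nor an effect of the added drug, so these inputs are assumptions:

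- true success without added treatment is 95% in one arm and 85% in the other, exactly at the limit;
- a share c of would-be failures becomes a success through the added drug, the same in both arms;
- n = 58 per arm.

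The recorded rate in each arm is p + (1 − p)c, so the recorded difference is 0.10 × (1 − c). The limit is met when difference + 1.645 × SE < 0.10, with SE² = [p1(1 − p1) + p2(1 − p2)]/58. The chance of that was found by enumerating all binomial outcomes (exact, Wald limit), and by the normal approximation Φ[(0.10 − difference)/SE − 1.645].

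| c | Recorded rates | Difference | Normal approx. | Exact |
|---|---|---|---|---|
| 0 | 95.0% vs 85.0% | 10.0 points | 5.0% | 6.9% |
| 10% | 95.5% vs 86.5% | 9.0 | 7.3% | 9.8% |
| 25% | 96.25% vs 88.75% | 7.5 | 13.0% | 16.6% |
| 50% | 97.5% vs 92.5% | 5.0 | 34.4% | 40.5% |

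For example, at c = 50%: SE = √[(0.024375 + 0.069375)/58] = 0.0402, and Φ(0.05/0.0402 − 1.645) = Φ(−0.40) = 34.4%.

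In children, the poorer arm has 58 × 0.15 = 8.7 would-be failures. The 10%, 25% and 50% rows thus convert about 0.9, 2.2 and 4.4 children in that arm.

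**The case against.** Several stronger readings are tempting, and the documents do not support them.

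- **That these children receive a non-study antibiotic.** Section 3.8 says so only for clinical failures.
- **That treatment starts before 96 h because susceptibility is known from day 1.** The flow chart in Appendix 2 marks the susceptibility test under day 1 but not when a result is available. Section 3.8 ties the choice of drug to the isolates that define the failure. No start time is given.
- **That azithromycin is the arm that gains.** The Background says of single-dose therapy that it works "although bacterial eradication is slower than with multiple dose therapy", but that remark concerns tetracycline and doxycycline. On the study drugs the Background points the other way: high azithromycin stool concentrations, azithromycin regarded as bactericidal, erythromycin as generally bacteriostatic. Figures that convert children in the azithromycin arm only therefore have no basis here.
- **That inferiority is hidden altogether.** A child positive on day 3 is already a failure on the bacteriologic primary outcome, whatever treatment follows, and culture positivity is compared on each study day.

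It can also be said that conversion may be close to nil. A child must be culture-positive, still purging, treated before 96 h and improved in the hours left; on a 24 h culture delay that leaves 0 to 24 h. This stands for the 96 h component, but not for prevented relapse.

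Finally, scoring after additional treatment is often left to a statistical analysis plan, and counting cessation regardless of later antibiotics is a recognised choice. But this protocol writes out its primary endpoint in section 7, and together with section 3.8 that definition credits the added drug's effect to the study drug. If that is intended, the protocol should say so.

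**Conclusion.** The point holds for the clinical outcome. As written, a child can be a clinical success after further antibiotic treatment for a positive culture, through cessation by 96 h or through a relapse that did not occur. If the slower-clearing arm is also the clinically poorer one, this shrinks the difference on the endpoint used for sizing.

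The size is conditional. At a true 10-point deficit, the chance of meeting the limit rises from 6.9% to between 9.8% and 40.5% as conversion in both arms goes from 10% to 50%. It does not change if nobody is converted. The conversion shares and the 85% rate are assumptions, and the documents identify neither the affected arm nor the start of treatment. The change is worth making because it is cheap and the possible bias favours the claim under test; the documents do not show that the bias will occur.

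**What to change.** Leave the care rule in section 3.8 as it is and change only the scoring.

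1. Add to 7.1 and 7.2: *A child given any additional antibiotic active against V. cholerae, beyond the assigned regimen, before watery stool has ceased is not a clinical success.* This wording applies whichever drug is chosen.
2. In the duration and daily-resolution analyses, treat such a child as unresolved from the first dose of the added antibiotic.
3. Add a sensitivity analysis that counts any child given such an antibiotic before follow-up as a non-success. The sentence in item 1 does not reach a child whose stool had already stopped and whose relapse may have been prevented.
4. Record the start time of the added antibiotic on the data form, since the protocol does not say that it is captured, and list these children by arm.

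The cost is a few sentences and one data field. Success rates will be slightly lower in both arms, because some of these children would have stopped in time anyway, and the clinical outcome will depend a little more on the culture result that triggers treatment. The planned 58 per arm is unchanged if 95% success still holds under the stricter definition.

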4. OUTCOME MEASURES

As measures of effectiveness, the following outcome measures will be compared:

4.1 Primary outcome measures

- Rates of clinical success
- Rates of bacteriologic success

4.2 Secondary outcome variables

- Duration of diarrhoea
- Rates of clinical relapse
- Rates of bacteriologic relapse
- Duration of fecal excretion of *V. cholerae*-O1 or *V. cholerae* O139
- Six-hourly, daily and total volume of watery stool during the study period
- Proportion of patients requiring unscheduled intravenous fluids
- Frequency of vomiting and its volume
- Resolution of diarrhoea among patients in two treatment groups on each study day

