2.1 Inclusion criteria

- Age / Gender: 1-15 years (male) or 5-15 years (female)
- Duration of illness: 24 hours or less
- Written informed consent for participation in the study from either parent/ guardian
- Severe dehydration according to WHO guidelines [32]
- Positive stool dark-field microscopic examination for *V. cholerae* (pre-enrollment), and isolation of *V. cholerae* O1 or O139 (post-enrollment) from a pre-therapy stool and/or rectal swab culture.

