3.7 Clinical evaluation and laboratory studies

Study patients will be hospitalized for full five days beginning from the time of initiation of study drug therapy. The following clinical and laboratory evaluations will be performed on the study patients at various time period of the study:

- **Weighting:** Before rehydration, after rehydration, just before initiation of the study drug (after the 4-hour observation period), every 24 hours during hospitalization, and at follow-up.
- **History and physical examination:** Before rehydration, after rehydration, at the time of initiation of study drug therapy, daily during hospitalization, and at follow up. In addition to evaluation of hydration status, the history and physical examinations will also focus on adverse events including vomiting, gastrointestinal distress, and rash.
- **Vital signs:** Rectal or oral temperature, pulse and respiratory rates, and blood pressure will be recorded before rehydration, after rehydration, just before administration of study drug, and then every 6 hours during hospitalization.
- **Quantitation of stool volume and/or weight:** This will be done for the rehydration and the observation periods, and for each 6 hour period of hospitalization.

- **Stool character:** Stool will be characterized as follows:
 - Watery:** Stool that can be poured like water
 - Soft:** Stool that cannot be poured, but that takes the shape of the container.
 - Formed:** Stool that retains its shape.
- **Stool culture for *V. cholerae* O1, O139 and non-O1; and *Shigella* and *Salmonella*:** Will be done before initiation of drug therapy on the day of admission, on study day 3, and at follow up 7 days after discharge from the hospital.
- **Rectal swab culture for *V. cholerae*:** Will be done before initiation of the study drug on the day of admission, and daily during hospitalization.
- **Hematologic studies:** Serum electrolytes, creatinine, hematocrit, and serum Sp.gr. will be measured before and after rehydration, and at 24 hours from the time of initiation of study drug therapy. Complete blood count and platelet count will be performed only once, after initial rehydration, however, may also be done at other time(s) if clinically indicated. A total of 2.5 ml + 3.0 ml + 2.5 ml of venous blood will be collected at above specified times.

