Laboratory facilities: The clinical laboratory services of the Laboratory Sciences Division of ICDDR,B will be used for all study related laboratory investigations (tests). These laboratories are regularly used for all protocols of the Centre.

Equipments: No equipment other than those required for routine clinical examination of children will be required for this study.

Data Analysis

Describe plans for data analysis. Indicate whether data will be analyzed by the investigators themselves or by other professionals. Specify what statistical softwares packages will be used and if the study is blinded, when the code will be opened. For clinical trials, indicate if interim data analysis will be required to monitor further progress of the study. (TYPE WITHIN THE PROVIDED SPACE).

1. Comparability of study groups

1.1 Before administration of the study drug: Age, dehydrated body weight, degree of dehydration, diarrhoea duration, vomiting frequency, and stool output during the rehydration and observation periods as well as other admission characteristics will be compared between the groups.

1.2 Comparison of primary outcome measures: Rates of clinical and bacteriologic success in the two treatment groups will be compared.

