1.3 Comparison of the secondary outcome measures

- Rates of clinical and bacteriologic relapse.
- Duration of diarrhoea in hours, and duration of fecal excretion of *V. cholerae* O1 or O139 in days.
- Volume of watery/liquid stool for each 6 and 24 hour of the study, and also the total amount of watery/liquid stools during the study period.
- Frequency of vomiting and the amount of vomitus, and proportion of patients with vomiting on each study day.
- Intake of oral and intravenous fluids for each 24 hour as well as the entire duration of the study.
- Proportion of patients with resolution of diarrhoea on each study day.
- Proportion of patients with a positive culture for infecting *V. cholerae* O1 or O139 on each study day.

2. Statistical methods

Data will be entered onto computer using SPSS for Windows (Version 6.0). Range check and double-entry system will be employed to facilitate data editing and cleaning. The significance of differences in continuous variables will be assessed by Student's t test for data that are normally distributed, or by Mann-Whitney U test for data which are not normally distributed. Significance of differences in the proportions will be assessed by the chi-square test, and Fisher's exact test will be employed when the expected number in any cell in the comparison is 5 or less. Survival analysis (Log Rank Test) will be done for the duration variables such as the proportions of patients with diarrhea, and a positive stool culture for *V. cholerae* O1 or O139 on each day of the study.

Ethical Assurance for Protection of Human Rights

Describe in the space provided the justifications for conducting this research in human subjects. If the study needs observations on sick individuals, provide sufficient reasons for using them. Indicate how subject's rights are protected and if there is any benefit or risk to each subject of the study.

Justifications for conducting this research in human subjects

This objective of this study is to compare clinical and bacteriologic efficacy as well as adverse events in association with therapy for children with clinically severe cholera with a single dose of azithromycin oral suspension with a 3-day course of erythromycin. Both of the study drugs are registered with the Drug Administration, Peoples' Republic of Bangladesh for use in the country.

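### Secondary stool output is stated as volume, without per-kg scaling or baseline adjustment, in children aged 1-15 years: the test is valid but loses precision

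*Protocol*

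**What the plan says.** Protocol section 4.2 names as a secondary outcome "Six-hourly, daily and total volume of watery stool during the study period". Data Analysis item 1.3 repeats it as "Volume of watery/liquid stool for each 6 and 24 hour of the study", together with the total over the study, and the project summary also speaks of total volume. None of these places gives a unit or divides by body weight.

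The test comes from one general rule in Data Analysis item 2 (Statistical methods), which assigns every continuous variable to "Student's t test for data that are normally distributed, or by Mann-Whitney U test for data which are not normally distributed". No covariate-adjusted analysis is named.

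The data for a sharper comparison are collected. Section 3.7 has children weighed before and after rehydration and "just before initiation of the study drug (after the 4-hour observation period), every 24 hours during hospitalization". On stool quantity the same section says: "This will be done for the rehydration and the observation periods, and for each 6 hour period of hospitalization". In the analysis, Data Analysis item 1.1 gives the pre-drug values one use only, a check of comparability: "stool output during the rehydration and observation periods as well as other admission characteristics will be compared between the groups". Dehydrated body weight is in the same list.

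Section 2.1 sets the age range at "1-15 years (male) or 5-15 years (female"). The project summary and section 3.3 define severity for entry per kg: at least 20 ml/kg in four hours, or 5.0 ml/kg per hour. Section 3.5 describes randomization in blocks of four and mentions no stratification by age or weight.

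**The concern.** Stool volume depends on body size as well as on disease and drug. A comparison in plain volume carries the spread of body weights as noise. The pre-treatment purging rate, which is likely to be prognostic, is measured in every child and then left out of the treatment comparison. The protocol treats purging as a per-kg quantity when it selects patients and drops that scaling when it names the outcome.

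Precision matters in this trial because the hypothesis is that the single dose is as effective as the three-day course. A non-significant difference on a needlessly noisy outcome is easily misread as support for similarity. If the arms happen to differ in weight, a difference in volume, or its absence, cannot be read directly as a drug effect.

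**Working it through.** **The plan's own figure.** Section 3.6 gives n = 2P(1-P)(Zα + Zβ)²/d². With P = 0.95, Zα = 1.645, Zβ = 0.8416 and d = 0.10, this is 2 × 0.95 × 0.05 × (2.4866)² / 0.01 = 58.74. The protocol states 58 per arm, so the figure is reproduced apart from rounding down. It concerns clinical success. The protocol gives no figure for stool volume.

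**Inputs.** From the Protocol: 58 per arm, ages 1-15 years, unadjusted tests. Assumed, because the documents give no values:
- SD of log weight, s_w: 0.3-0.5. Weights spread evenly on the log scale over 8-25 kg give ln(25/8)/√12 = 0.33; over 8-40 kg, ln(5)/√12 = 0.465. The dose maxima in section 3.5 take effect at 500/12.5 = 40 kg and 1000/20 = 50 kg, so the protocol provides for children that heavy.
- SD of log ml/kg output, s_k: 0.5-0.7.
- Correlation r between pre-treatment purging and later output: 0.3-0.7.
- Per-kg output independent of weight.

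**Variance.** Volume = weight × output per kg. On the log scale:
- plain volume: s_w² + s_k²
- per kg: s_k²
- per kg, adjusted for baseline purging: s_k²(1 - r²)

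| s_w | s_k | volume ÷ per kg | volume ÷ adjusted, r = 0.3 | r = 0.5 | r = 0.7 |
|---|---|---|---|---|---|
| 0.3 | 0.5 | 1.36 | 1.49 | 1.81 | 2.67 |
| 0.3 | 0.7 | 1.18 | 1.30 | 1.58 | 2.32 |
| 0.4 | 0.5 | 1.64 | 1.80 | 2.19 | 3.22 |
| 0.4 | 0.7 | 1.33 | 1.46 | 1.77 | 2.60 |
| 0.5 | 0.5 | 2.00 | 2.20 | 2.67 | 3.92 |
| 0.5 | 0.7 | 1.51 | 1.66 | 2.01 | 2.96 |

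For example, s_w = 0.3 and s_k = 0.7 give (0.09 + 0.49)/0.49 = 1.18, and 1.18/(1 - 0.09) = 1.30.

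**Power.** Take a 30% reduction in output as an illustration, with 58 per arm, r = 0.5 and 4,000 simulated trials per setting (s_w 0.3 or 0.5, s_k 0.5 or 0.7):

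| Analysis | Power |
|---|---|
| Volume, t test | 46-84% |
| Volume, Mann-Whitney | 59-89% |
| ml/kg, t test | 68-95% |
| ml/kg, Mann-Whitney | 75-96% |
| log ml/kg, adjusted for baseline purging | 87-99% |

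**Type I error.** With no true effect, every method rejected in 4.3-5.4% of trials.

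**Weight imbalance.** The 95% limit for a chance gap in geometric mean weight is exp(1.96 × s_w × √(2/58)) - 1. That is 11.5% for s_w = 0.3 and 20.0% for s_w = 0.5. In the roughly 5% of null trials beyond this limit, Mann-Whitney on volume rejected in 12-30%, against 5-9% for ml/kg. These conditional rates are rough, since they rest on about 200 trials per setting (0.05 × 4,000).

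**The case against.** The strongest reply is that the protocol leaves the unit open. It says volume, gives no unit for the outcome, and uses ml/kg wherever it does give a unit for stool output, so a separate analysis plan could scale it. This stands in part: a plain-volume analysis is the natural reading of section 4.2 and Data Analysis item 1.3, not something they state outright. But the protocol does name the outcome and the test, and neither brings in weight or baseline output.

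A reader might infer that weight imbalance makes the comparison biased or inflates false positives. The documents do not support that. Allocation is randomized, weight variation is already in the standard error, and overall type I error stays at about 5%. The excess rejection is conditional on an unusual allocation, which the baseline comparison in Data Analysis item 1.1 would show.

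A reader might also take stool volume to be the trial's main continuous efficacy measure. Section 4.2 does not rank its outcomes and lists duration of diarrhoea first. Nor does the protocol say that some 20 separate six-hourly tests will be run. That number is only five days times four periods.

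The size of the gain is also open to challenge. If log per-kg output falls with log weight with slope -b, weight adds (1-b)²s_w² to the variance of volume and b²s_w² to that of per-kg output. These are equal at b = 0.5, where scaling alone gains nothing. The entry threshold of 5.0 ml/kg per hour also truncates the baseline covariate and may weaken its correlation with outcome. Both points stand as limits on the size.

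**Conclusion.** The point holds as one of efficiency and interpretability on a secondary outcome. The planned tests are valid, and neither the two primary success rates nor the sample size is touched. Under the stated assumptions, per-kg scaling alone reduces variance by a factor of about 1.2-2.0, and scaling plus adjustment for pre-treatment purging by about 1.3-3.9. The gain from adjustment depends on a correlation that the documents do not give, and the gain from scaling depends on per-kg output being roughly independent of weight. The direction was the same throughout the range tried. Because the data are already collected, the improvement is worth making even at the low end.

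**What to change.** State in section 4.2 and Data Analysis item 1.3 that stool output is expressed as ml per kg of the post-rehydration weight taken just before study drug, with that one weight used throughout for each child. Name one main stool-output comparison: log total output (ml/kg) between arms by ANCOVA, with log observation-period output (ml/kg per hour) as covariate. Report the six-hourly and daily values descriptively or in one repeated-measures model. Those values will include zeros once watery stool stops, so the log scale suits the total better than the single periods.

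The cost is a little more analysis. Weight and observation-period output are already recorded under section 3.7, so no data collection changes.
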